# Re-priming/Re-escalation for Magrolimab

Given the large CD47 antigen sink on red blood cells, patients who have a long dose delay of magrolimab are required to be re-primed with magrolimab dosing to resaturate the CD47 antigen sink.

R/R and TN/U Cohorts: For patients who had a dose delay of greater than 4 weeks for magrolimab, re-priming/re-escalation is needed with magrolimab. For patients who have not received at least one 30 mg/kg dose of magrolimab (i.e., for patients who have either not received their first dose of 30 mg/kg or patients who have received doses < 30 mg/kg), a dose delay of only 2 weeks is allowed until re-priming is needed. Table 6-1 illustrates the re-priming/re-escalation magrolimab dosing regimen and schedule of assessments.

RBC Transfusion-dependent Low-risk MDS Cohort: For patients who had a dose delay of greater than 6 weeks for magrolimab, re-priming/re-escalation is needed with magrolimab. For patients who have not received at least one 30 mg/kg dose of magrolimab, a dose delay of only 2 weeks is allowed until re-priming is needed. For patients who have not received at least one 60 mg/kg dose of magrolimab, a dose delay of 4 weeks is allowed until re-priming is needed. Table 6-1 illustrates the re-priming/re-escalation magrolimab dosing regimen and schedule of assessments.

The re-priming/re-escalation dosing regimen for magnolimab is shown below in Table 6-1.

Table 6-1. Magrolimab/Azacitidine Re-priming/Re-escalation Dosing Schedule

		Dose Schedule (Day per 28-day Cycle)		
Cohort	Drug/Dose/Route	Re-priming Cycle	Subsequent Cycles	
R/R Cohort and TN/U	Magrolimab - 1 mg/kg IV	Day 1, 4	_	
Cohort (including the TP53 Mutant TN/U AML Subcohort)	Magrolimab - 15 mg/kg IV	Day 8		
, and sassinsity	Magrolimab - 30 mg/kg IV	Day 11, 15, 22	Day 1, 15	
	Azacitidine - 75 mg/m² SC or IV b	Day 1-7	Day 1-7	
R/R MDS Magrolimab Monotherapy Cohort c	Magrolimab - 1 mg/kg IV	Day 1, 4	_	
Monotherapy Conort	Magrolimab - 15 mg/kg IV	Day 8	_	
	Magrolimab - 30 mg/kg IV	Day 11, 15, 22	Day 1, 15	
RBC Transfusion-	Magrolimab - 1 mg/kg IV	Day 1	_	
dependent Low-risk Cohort	Magrolimab - 30 mg/kg IV	Day 8, 15, 22	_	
	Magrolimab - 60 mg/kg IV a	_	Day 1	
	Azacitidine - 75 mg/m² SC or IV b	Day 1-5	Day 1-5	

Abbreviations: CTSC = Clinical Trial Steering Committee; IV = intravenous; MDS = myelodysplastic syndrome; RBC = red blood cell; R/R = relapsed/refractory; SC = subcutaneous; TN/U = treatment-naïve/unfit (for standard induction chemotherapy); UK = United Kingdom; US = United States.

#### 6.1.2. Azacitidine

Azacitidine will be administered according to region-specific drug labeling, either SC or IV, at the standard dose of 75 mg/m^2 on Days 1 to 7 of each 28-day cycle for the R/R (except the magrolimab monotherapy cohort, which will allow the addition of azacitidine after the first response assessment with Investigator and Sponsor agreement) and TN/U cohorts (including TP53 mutant cohort) for all dose levels of magrolimab when

a. The magrolimab dosing of 60 mg/kg, 45 mg/kg, or other alternative dose will be utilized based on the safety run-in data and CTSC decision for expansion.

b. Azacitidine will be administered per region-specific labeling: SC in UK or US; IV in US only.

c. For R/R MDS Magrolimab Monotherapy patients who require repriming, and are receiving both magrolimab and azacitidine post Cycle 3, the repriming schedule is Azacitidine - 75 mg/m² SC or IV, Day 1-7 of the repriming Cycle.

azacitidine is scheduled to be administered (for patients assigned to combination treatment). For the RBC Transfusion-dependent Low-risk MDS Cohort, azacitidine will be administered either SC or IV at the dose of 75 mg/m² on Days 1 to 5 of each 28-day cycle (see Table 3-3) for all dose levels of magrolimab when azacitidine is scheduled to be administered (for patients assigned to combination treatment). When administered IV, the total dose of azacitidine (diluted in a 50-100 mL infusion bag of either 0.9% Sodium Chloride Injection or Lactated Ringer's Injection solution) is infused over a period of 10 to 40 minutes (refer to the azacitidine prescribing information for detailed instructions for preparation and administration).

#### 6.1.3. Premedication

Premedication is required prior to the administration of the first 4 doses of magrolimab and in case of reintroduction with re-priming for all cohorts except the RBC Transfusion-dependent Low-risk Cohort, for which premedication is required for the first 2 doses of magrolimab and the first 2 doses in case of reintroduction with re-priming. Premedication for subsequent magrolimab treatments may be continued based on the treating physician's clinical judgement and the presence/severity of prior infusion-related reactions. In the case of a Grade 3 infusion-related reaction, a premedication regimen for subsequent treatments is required (Section 6.2.2.1).

Recommended premedications are oral acetaminophen 650 to 1000 mg and oral or IV diphenhydramine 25 to 50 mg, or comparable regimen. If less than 4 hours has elapsed since a prior dose of acetaminophen has been given, the dose of acetaminophen premedication may be omitted.

# 6.2. Dose Modifications, Dose Delays, and Safety Management Guidelines

# 6.2.1. Dose Modification and Delay Guidelines

## 6.2.1.1. Magrolimab

## **Dose Modifications**

Magrolimab may be withheld if treatment-emergent and/or magrolimab-related AEs occur, which include all AEs that constitute a DLT, as defined in Section 3.3.5.

Magrolimab may be reintroduced at a 50% dose reduction if the severity has recovered to Grade  $\leq$  2 within 4 weeks and in the absence of disease progression, with approval from the Medical Monitor. A dose delay for up to 3 days may be permissible if the patient's WBC count is greater than 20 × 10 $^9$ /L (which is applicable to Cycle 1), to allow for oral hydroxyurea or etoposide treatment to reduce the WBC count. Further dose delay due to elevated WBC counts must be discussed and approved by the Medical Monitor.

Patients who experience a Grade 4 or higher AE of hemagglutination and/or microangiopathy related to magrolimab will permanently discontinue magrolimab treatment. Patients who experience Grade 3 hemagglutination and/or microangiopathy will have magrolimab dosing withheld, and may be reintroduced at a 50% dose reduction if the event severity recovers to Grade  $\leq$  1 within 4 weeks and there is no evidence of disease progression.

With one exception, patients who experience a DLT will have their treatment held for up to 4 weeks to allow sufficient time for recovery, but may restart dosing at a lower dose level if they still meet study eligibility criteria. Patients who experience a DLT of Grade 4 non-hematological toxicity will not restart magrolimab and will be withdrawn from study drug treatment. Data from patients who restart dosing after the recovery period will not contribute to the MTD evaluation at the lower dose level. Treatment delays of more than 4 weeks (such as for an unrelated medical condition with expected recovery) must be discussed with the Medical Monitor and approved by the Sponsor.

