# **Treatment Interruption and Delays**

A magrolimab treatment interruption is defined as a nonprotocol-specified interruption from treatment, assessments, and procedures. Ongoing data analysis across magrolimab + azacitidine trials shows that Q2W dosing of magrolimab without significant interruptions is important to yield optimal efficacy. Therefore, when a patient has an azacitidine treatment delay due solely to azacitidine-related toxicities, magrolimab should continue with Q2W dosing as scheduled (Table 7-4) or Q4W dosing as scheduled (Table 3-3). Re-initiation of azacitidine will start at the next cycle (which is

numerically after the azacitidine cycle which the patient most recently received azacitidine prior to the dose delay). Patients will proceed with this cycle starting on Day 1. Response assessments should occur at time points associated with cycles of azacitidine per Schedules of Assessments (Table 7-1, Table 7-2, and Table 7-3) (e.g., Cycle 3 Day 1 response assessment should only occur after a patient has received 2 cycles of azacitidine). Additionally, in the event that magrolimab dosing is decoupled from azacitidine dosing, collection of PK and ADA should always coincide with magrolimab dosing at time points specified in Table 7-4. Patients in Cycle 1 of the TN/U Expansion or RBC Transfusion-dependent Low-risk MDS Cohorts should follow dosing guidelines and collections for that cycle. Patients in Cycle 2 of TN/U Expansion Cohort should follow dosing schedule and collections for that cycle. Patients in Cycle 3 or beyond should follow Q2C collection of PK and ADA.

Patients with a magrolimab interruption of longer than 4 weeks (4 weeks is maximum allowed for an elective drug delay) or a treatment delay of longer than 4 weeks must undergo intrapatient dose escalation of magrolimab again based on their original dosing regimen (e.g., for patients on once-weekly dosing, 1 mg/kg priming dose on Days 1 and 4, 15 mg/kg on Day 8, and 30 mg/kg on Days 11, 15, and 22; or for Rollover patients who remain on twice-weekly maintenance dosing, 1 mg/kg priming dose on Days 1 and 4, 15 mg/kg on Day 8, and 30 mg/kg on Days 11, 15, 18, 22, and 25).

Any treatment delays/interruptions should be discussed with the Medical Monitor and approved by the Sponsor.

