   Grade 3 is described as prolonged infusion-related reactions (e.g., not rapidly responsive to symptomatic medication and/or brief interruption of infusion), or recurrence of symptoms following initial improvement, or where hospitalization is indicated for other clinical sequelae (e.g., renal impairment, pulmonary infiltrates).
   Grade 4 is described as having life-threatening consequences and where urgent intervention is indicated.
  - Immediately discontinue infusion of magrolimab.

- Begin an IV infusion of normal saline, and consider treating the patient as follows: Administer bronchodilators, epinephrine 0.2 to 1 mg of a 1:1,000 solution for SC administration or 0.1 to 0.25 mg of a 1:10,000 solution injected slowly for IV administration and/or diphenhydramine 50 mg IV with methylprednisolone 100 mg IV (or equivalent), as needed.
- The patient should be monitored until the Investigator is comfortable that the symptoms will not recur.
- Patients who have Grade 4 infusion-related reactions occurring with the first dose
   (priming dose) will be permanently discontinued from study treatment.
- Patients who experience Grade 3 infusion-related reactions must be given premedication prior to subsequent doses. In this setting, premedication with oral acetaminophen (650-1000 mg), oral or IV diphenhydramine (25-50 mg), and IV dexamethasone (4-20 mg), or a comparable regimen, is recommended for the subsequent 2 doses. Continued premedication with corticosteroids beyond these 2 doses may be administered at the discretion of the treating physician.
- Patients who receive premedication (with the regimen above, including corticosteroids) and still experience a Grade 3 or 4 infusion-related reaction will be permanently discontinued from study treatment.
- For anaphylaxis, Investigators should follow their institutional guidelines for treatment.
- All patients with Grade 3 or greater infusion-related reactions will be observed until the AE resolves or stabilizes, with vital sign measurements and additional evaluations as medically indicated for the management of the AEs.

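### Magrolimab restart and re-priming rules conflict: two restart rules for a DLT, no carry-forward of a patient's dose reduction at re-priming, and two re-priming triggers for low-risk MDS

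*Protocol*

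**What the plan says.** Three parts of the protocol govern what a patient receives when magrolimab is resumed.

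- **Section 6.2.1.1, Dose Modifications, opening.** Magrolimab may be withheld for treatment-emergent or related adverse events, "which include all AEs that constitute a DLT, as defined in Section 3.3.5". Then "Magrolimab may be reintroduced at a 50% dose reduction", provided that the event has recovered to Grade 2 or lower within 4 weeks, the disease has not progressed and the Medical Monitor approves.
- **Section 6.2.1.1, Dose Modifications, DLT paragraph.** Treatment is held for up to 4 weeks after a DLT, and the patient "may restart dosing at a lower dose level if they still meet study eligibility criteria". No percentage or recovery grade is given.
- **Section 6.2.1.1, Treatment Interruption and Delays.** A patient with an interruption of more than 4 weeks or "a treatment delay of longer than 4 weeks must undergo intrapatient dose escalation of magrolimab again based on their original dosing regimen". The worked examples end at 30 mg/kg. No cohort limit is stated.
- **Section 6.1.1, Re-priming/Re-escalation, with Table 6-1.** For the R/R and TN/U cohorts: "For patients who had a dose delay of greater than 4 weeks for magrolimab, re-priming/re-escalation is needed with magrolimab". Before a first 30 mg/kg dose the trigger is 2 weeks. For low-risk MDS the general trigger is more than 6 weeks, with 4 weeks before a first 60 mg/kg dose and 2 weeks before a first 30 mg/kg dose. Table 6-1 ends at 30 mg/kg, or at 60 mg/kg for low-risk MDS. Its footnote a changes the 60 mg/kg figure only for a cohort-level CTSC decision.

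**The concern.** These are instructions for re-exposure after toxicity, so they should lead every site to the same dose for the same history. They do not. One paragraph fixes the size of the cut after a DLT and another leaves it open under a different condition. The re-priming text, which says that the patient must re-escalate, sends everyone to the unreduced regimen and never mentions a patient whose dose was cut for toxicity. Two sites that both follow the protocol can therefore reach maintenance doses that differ two-fold. Exposure and adverse events after a dose modification then do not reflect a single rule, and Section 11.1 relies on summaries of both.

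**Working it through.** No power or error-rate figure is involved. The check sets the rules side by side and does the dose arithmetic.

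**Step 1. Maintenance dose reached under each rule (mg/kg).**

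| Rule | Condition | R/R and TN/U (30) | Low-risk MDS (60) |
|---|---|---|---|
| A. 50% cut (6.2.1.1, opening) | Recovery to Grade 2 or lower within 4 weeks | 0.5 × 30 = 15 | 0.5 × 60 = 30 |
| B. Lower dose level (6.2.1.1, DLT paragraph) | DLT, hold of up to 4 weeks, still eligible | TN/U Dose Evaluation only; not fixed | Not fixed |
| C. Re-priming (6.2.1.1 and Table 6-1) | Delay beyond the trigger | 30 | 60, or the cohort dose set by the CTSC |

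**Step 2. What rule B can mean.** Section 3.3.5 limits DLTs to the TN/U Dose Evaluation and low-risk MDS cohorts. Table 3-2 lists no level below Level 1. Section 3.3.2 allows cohort decrements of up to 50%, which from 30 mg/kg gives anything from 15 to just under 30. For low-risk MDS, Table 3-3 has a de-escalation row at 45 mg/kg (45/60 = 75%, a 25% cut), and its footnote c also allows an alternative below 60, naming 30 mg/kg Q2W. All of these are cohort-level decisions. None defines the level for one patient restarting after a DLT.

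**Step 3. Sequence of A then C.** A patient on 30 mg/kg has a Grade 3 event that recovers in time and restarts at 15 mg/kg under rule A. Months later the patient misses more than 4 weeks for another reason. Rule C now applies, and it refers to the original regimen. The patient is re-primed from 1 mg/kg and reaches 30 mg/kg, and 30/15 = 2. For low-risk MDS at 60 mg/kg the corresponding figures are 30 and 60, also a ratio of 2. Footnote a of Table 6-1 does not prevent this, because it follows the cohort's dose and not the patient's.

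**Step 4. Overlap of A and C in one event.** Rule A runs to 4 weeks and rule C usually starts after 4 weeks, so for most patients they do not meet. Before a first 30 mg/kg dose, however, rule C starts after 2 weeks, and delays of more than 2 and up to 4 weeks satisfy both. Example: a TN/U Dose Evaluation patient has a Grade 3 DLT before the first 30 mg/kg dose, is held for 3 weeks and recovers to Grade 2. If still eligible, this patient meets rules A, B and C together. The text also does not say to which dose the 50% applies in a patient who is still escalating.

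**Step 5. Trigger for low-risk MDS.** For a patient who has had at least one 60 mg/kg dose, Section 6.1.1 calls for re-priming after more than 6 weeks and Section 6.2.1.1 after more than 4. A 5-week delay requires re-priming under one and not under the other. The cohort is not outside the scope of the 6.2.1.1 subsection, which itself refers to Q4W dosing and Table 3-3.

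**The case against.** The best reply is that the two DLT statements can be read together, one saying that the dose is lower and the other by how much. For TN/U a 50% cut lies within the permitted range. The 45 mg/kg row is a cohort step, and its footnote names 30 mg/kg too. DLTs were assessed early and in few patients: TN/U Dose Evaluation closed after 8, and Table 7-3 limits low-risk assessment to the first 6 weeks of the safety run-in. Delays need discussion with the Medical Monitor and Sponsor approval. On re-priming, the protocol is silent about reduced patients and does not say that they return to full dose.

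Much of this stands. It narrows the DLT conflict to two cohorts and to an undefined level, with differing conditions. It does not answer the re-priming point: the text says that the patient must re-escalate on the original regimen, which for a reduced patient is an instruction and not silence. Approval limits divergence between sites but gives the approver no rule to apply.

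A reader might infer more than the documents support:

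- *That 30 and 45 mg/kg are contradictory restart doses for low-risk MDS.* The 45 mg/kg row is not a rule for an individual patient.
- *That a toxicity lasting 5 weeks returns to full dose while one lasting 3 weeks gets half.* Reintroduction after toxicity is tied to recovery within 4 weeks, and the example given for longer delays is an unrelated condition. The protocol does not state this outcome.
- *That patients restart at full dose on the first day.* Re-priming starts at 1 mg/kg.
- *That the Grade 4 infusion-reaction text contradicts the DLT rule.* Section 6.2.2.1 requires discontinuation for "Patients who have Grade 4 infusion-related reactions occurring with the first dose", or for a Grade 3 or 4 reaction despite premedication that included corticosteroids. It nowhere permits re-dosing after other Grade 4 reactions, so it can be followed together with "Patients who experience a DLT of Grade 4 non-hematological toxicity will not restart magrolimab and will be withdrawn from study drug treatment".

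**Conclusion.** The point holds in three parts.

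1. Section 6.2.1.1 gives two restart rules for a DLT, with different conditions and a lower level that is undefined for the individual patient. This affects only the TN/U Dose Evaluation and low-risk MDS cohorts.
2. Re-priming has no provision for an earlier patient-level reduction. Read literally, it undoes that reduction: 30 instead of 15 mg/kg, or 60 instead of 30 mg/kg where 60 is the cohort dose. Before a first 30 mg/kg dose, the re-priming rule and the 50% rule can also apply to the same event. This part is not limited to the DLT cohorts, and closing enrollment does not end it for patients still on treatment.
3. The low-risk MDS trigger is stated as more than 6 weeks and as more than 4 weeks.

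The second part is the most important. It rests on taking the reference to the original regimen at its word and on finding no exception for reduced patients in Section 6.1.1, Section 6.2.1.1 or Table 6-1. The protocol does not report how many patients have had a reduction or a qualifying delay, so the number affected is unknown. No effect on the CR analysis or the sample size is claimed.

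**What to change.** The sponsor and CTSC should reconcile Section 6.1.1 (re-priming text, Table 6-1 and footnote a) with Section 6.2.1.1 (Dose Modifications; Treatment Interruption and Delays), and make these changes:

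- Replace the two DLT restart statements with one rule that states the size of the change, the dose to which it applies and the condition for restarting. If a lower dose level is kept, define it for an individual patient and check it against Sections 3.3.2, 3.4 and 3.4.1 and Table 3-3.
- State in Table 6-1 and in the interruption paragraph how an existing patient-level reduction is handled at re-priming.
- State which instruction governs when the 2-week re-priming trigger falls inside the 4-week recovery window.
- Give one re-priming trigger per cohort and use it in both sections.

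Which dose, level or interval applies is for the sponsor and CTSC to decide; none is proposed here. The cost is a clarification letter or amendment wording, with no added patients, visits or procedures.

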# **Treatment Interruption and Delays**

A magrolimab treatment interruption is defined as a nonprotocol-specified interruption from treatment, assessments, and procedures. Ongoing data analysis across magrolimab + azacitidine trials shows that Q2W dosing of magrolimab without significant interruptions is important to yield optimal efficacy. Therefore, when a patient has an azacitidine treatment delay due solely to azacitidine-related toxicities, magrolimab should continue with Q2W dosing as scheduled (Table 7-4) or Q4W dosing as scheduled (Table 3-3). Re-initiation of azacitidine will start at the next cycle (which is

numerically after the azacitidine cycle which the patient most recently received azacitidine prior to the dose delay). Patients will proceed with this cycle starting on Day 1. Response assessments should occur at time points associated with cycles of azacitidine per Schedules of Assessments (Table 7-1, Table 7-2, and Table 7-3) (e.g., Cycle 3 Day 1 response assessment should only occur after a patient has received 2 cycles of azacitidine). Additionally, in the event that magrolimab dosing is decoupled from azacitidine dosing, collection of PK and ADA should always coincide with magrolimab dosing at time points specified in Table 7-4. Patients in Cycle 1 of the TN/U Expansion or RBC Transfusion-dependent Low-risk MDS Cohorts should follow dosing guidelines and collections for that cycle. Patients in Cycle 2 of TN/U Expansion Cohort should follow dosing schedule and collections for that cycle. Patients in Cycle 3 or beyond should follow Q2C collection of PK and ADA.

Patients with a magrolimab interruption of longer than 4 weeks (4 weeks is maximum allowed for an elective drug delay) or a treatment delay of longer than 4 weeks must undergo intrapatient dose escalation of magrolimab again based on their original dosing regimen (e.g., for patients on once-weekly dosing, 1 mg/kg priming dose on Days 1 and 4, 15 mg/kg on Day 8, and 30 mg/kg on Days 11, 15, and 22; or for Rollover patients who remain on twice-weekly maintenance dosing, 1 mg/kg priming dose on Days 1 and 4, 15 mg/kg on Day 8, and 30 mg/kg on Days 11, 15, 18, 22, and 25).

Any treatment delays/interruptions should be discussed with the Medical Monitor and approved by the Sponsor.

## **Maintenance Dose Schedule Modification**

Patients in the R/R and TN/U Cohorts who have completed at least 8 weeks of therapy may stay at the same infusion dose and will have their magrolimab schedule of administration modified to weekly as decided by the CTSC based on clinical, PK, and pharmacodynamic data. Patients in the Rollover Cohort may continue the same dose level and schedule (i.e., twice weekly) of magrolimab monotherapy as previously received in the Phase 1 AML study or may transition to once-weekly dosing. Patients who are being treated under the previous Amendment may transition to the new

(weekly) dosing schedule at the next cycle, or as determined by the Investigator. If a patient has only received Day 1 treatment for a cycle, the patient may transfer to the Q2W dosing regimen with that cycle, for the balance of the cycle and beyond.

